An Exploratory Prospective Trial of Rescue Acupuncture for the Treatment of
Acute Migraine.

NCT02764996

June 29, 2016

PROTOCOL FOR CLINICAL INVESTIGATION – NON-EXEMPT HUMAN
(Wilford Hall Ambulatory Surgical Center – WHASC)
PROTOCOL SUMMARY

1. Title:

An Exploratory Prospective Trial of Rescue Acupuncture for the Treatment of Acute Migraine.

FWH20150084H

2.0. Principal Investigator (PI):

WHASC PI:

Name	[name], D.O
Rank/Corps or Civilian Rating	Capt
Date of IRB Approved CITI Training & Date of Good Clinical Practice Training	07/09/15
Branch of Service	USAF
AD Mil/DoD Civilian/Ctr/Non-DoD Civ	AD MIL
Department & Base	Family Medicine Residency, Nellis AFB
Phone & [contact]
E-Mail Address & AKO/DKO E-Mail Address	[contact]

3.0. Research Plan:

3.1. Purpose:

To begin to determine if acupuncture is as effective as, or more effective than, rescue medication in the acute treatment of migraine.

3.2. Hypotheses, Research Questions or Objectives:

We will estimate the magnitude of effect that acupuncture has as an alternative to medication for treatment of acute migraine, as measured by change in headache pain severity 20-30 minutes, 2 hours, 4 hours 24 hours post treatment.

4. Brief Summary of the study:

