This will be an exploratory observational trial of rescue acupuncture for the treatment of acute migraine in military beneficiaries to gain information to inform the power analysis of a larger, more definitive trial. We do not seek to definitively answer the question of whether this acupuncture protocol is effective; rather, we seek to estimate the proportion of migraine episodes that result in headache-free status 20-30 minutes, 2 hours, 4 hours, and 24 hours after an acupuncture treatment. Acupuncture treatments will be subject dependent, and points could include the N point (on scalp); various auricular points to include Shen Men, Point Zero, thalamus and Omega-2; body points to include Liver 2, Liver 3, Gall Bladder 20, bladder 10; and surface release over tense areas in the neck or shoulders. Researchers will document the points used, and data will be aggregated to determine overall effectiveness. Sub-group analysis by points will be performed to determine if there is more usefulness in 1 point or combination of points. These estimates will inform statistical power calculations for a future randomized controlled trial (RCT) that directly compares the effectiveness of Rescue Acupuncture with medical management of acute migraine with rescue medication. We will also assess the feasibility of this study protocol as well as patient receptivity and satisfaction.

5. Subjects:

Male and female DoD beneficiaries ages 18 years or older will be recruited at the Mike O’Callaghan Federal Medical Center (MOFMC). No special populations (e.g., pregnant women, children, military basic trainees, prisoners, detainees) will be recruited.

6. Inclusion/exclusion criteria:

Inclusion:

- Male and female DoD beneficiaries, age 18 years or older, who have been previously prescribed rescue medication to treat their acute migraine episodes.

Exclusion:

- Pregnant
- Absence of ear
- Active cellulitis of ear
- Ear anatomy precluding identification of acupuncture landmarks
- Use of Hearing Aids that preclude the insertion of needles

- Use of anticoagulants
- Unable to drive during rapid onset of migraine or inability to find someone to drive you

7. Number of Subjects: TOTAL NUMBER OF SUBJECTS (nation-wide/study-wide): 60

8. Use of an Investigational New Drug: N/A

9. Use of an Investigational Device: Seirin J-Type Acupuncture needles and Sedatelec ASP Original Gold Acupuncture needles, 510(k) exempt as Class II device under 21 CFR 880.5580

10. Use of a Placebo: N/A

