- Review past medical history in Armed Forces Health Longitudinal Technology Application (AHLTA) to verify the inclusion/exclusion criteria including previous encounter, vital signs review, medication list, co-morbidities, demographics, problems list, and note any prior acupuncture received. (research only)
- Record: Date of birth, age, gender, race, ethnicity, last 4 of social security number, name of standard of care rescue medications (over-the-counter and prescription), current email address (to be used for scheduling only), height (in

inches), weight (in pounds), history of traumatic brain injury, concussion, or any mild to severe head trauma, medication use, history of acupuncture. (research only)

- We will ask what the subjects expectations are regarding acupuncture's effectiveness for migraine. (research only)
- We will instruct subjects not to take their over-the-counter and prescription headache medications until after their visit with the research staff. (Standard care)
- We will instruct subjects to bring their over-the-counter and prescription headache medications with them to each visit if their symptoms do not resolve from the acupuncture treatment. (research only)
- Patient will be instructed to contact the Research Coordinator, as soon as possible, after onset of migraine symptoms (including prodromal symptoms) to schedule an emergent visit with the research staff. (research only)
- Patient will be given a contact card with the names and phone numbers of the research staff to contact when they have a migraine episode.

Migraine Episode:

- Self-reported headache pain severity (0=no headache, 1=mild, 2=moderate, 3=severe) (Standard care)
- Record type and amount of rescue medications (over-the-counter and prescription) use in the past 7 days. (research only)
- Acupuncture treatments will be subject dependent, and points could include the N point (on scalp); various auricular points to include Shen Men, Point Zero, thalamus and Omega-2; body points to include Liver 2, Liver 3, Gall Bladder 20, bladder 10; and surface release over tense areas in the neck or shoulders. (Standard care)
- Researchers will document the points used. (Standard care)
*If after 20-30 minutes these patients have not had resolution of their headache, they may take their standard of care rescue medication. (research only)
- The subject will sit for 20-30 minutes post-acupuncture(research only), and then the needles will be removed and the subject will be asked:

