 - Self-reported headache pain severity (0=no headache, 1=mild, 2=moderate, 3=severe) (research only)
- Subject is allowed to leave and will be informed of the following telephone follow ups:
- 2 Hours post acupuncture:
 - Self-reported headache pain severity (0=no headache, 1=mild, 2=moderate, 3=severe) (research only)
- 4 Hours post acupuncture:
 - Self-reported headache pain severity (0=no headache, 1=mild, 2=moderate, 3=severe) (research only)
- 24 Hours post acupuncture:
 - Self-reported headache pain severity (0=no headache, 1=mild, 2=moderate, 3=severe)
 - Would you use acupuncture for future pain management? (Yes or no)
 - Would you prefer acupuncture or your rescue meds (both over-the-counter and prescription) for future episodes?
 - Record type and amount of rescue medications (over-the-counter and prescription) used since acupuncture. (research only)

Patients with missed phone calls will not be withdrawn from the study. If there is a missed call, we will mark as 'missed', including the reason and continue with the next phone call.

The Research Coordinator will record the name of the AI performing the acupuncture and also the placement of the acupuncture needles for each migraine episode.

Placement of Acupuncture:

[figure not shown]
Acupuncture treatments will be subject dependent, and points could include the N point (on scalp) (Figure 1); various auricular points to include Shen Men(Figure 2), Point Zero(Figure 3), thalamus(Figure 4) and Omega-2(Figure 5); body points to include Liver 2(Figure 6), Liver 3(Figure 6), Gall Bladder 20(Figure 7), bladder 10(Figure 7); and surface release over tense areas in the neck or shoulders. We will utilize the Seirin J-Type Acupuncture needles (Figure 98). Intermittent placement checks by the medical acupuncturist will be performed.

This study will follow all FDA requirements for the safe use of these devices.

Only the investigators listed on this study will perform the insertion of the acupuncture needles. All investigators are trained in this acupuncture technique and credentialed by the Credentials committees.

The Food and Drug Administration (FDA) regulates acupuncture needles as a class II medical device, because they are intended for use in the cure, mitigation, treatment, or prevention of disease in man or are intended to affect the structure or function of the body of man. The FDA regulates the acupuncture needles (see 21 CFR 880.5580), but not the practice of acupuncture itself.

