The needles being used are Seirin J-Type Acupuncture needles (Figure 8), which are exempt from premarket notification by the FDA for use in acupuncture and will be used in accordance with their FDA approved labeling.

3.6.1. Interventions, Observations, or Data Sought:

We will measure subject’s migraine pain level, doses of analgesics taken before intervention and at 20-30 minutes, 2 hours, 4 hours, and 24 hours post treatment. Additionally, we will measure patient centered outcomes and receptivity to acupuncture. Acupuncture treatments will be subject dependent, and points could include the N point (on scalp); various auricular points to include Shen Men, Point Zero, thalamus and Omega-2; body points to include Liver 2, Liver 3, Gall Bladder 20, bladder 10; and surface release over tense areas in the neck or shoulders. Researchers will document the points used, and data will be aggregated to determine overall effectiveness. Sub-group analysis by points will be performed to determine if there is more usefulness in 1 point or combination of points.

3.6.2. Data Collection and Processing:

Data will be collected and recorded in a spreadsheet. At the conclusion of the study, all personally identifying information will be removed prior to analysis.

3.6.3. Setting:

Male and female (DoD beneficiaries). Age 18 years or older, who currently take rescue medication to treat their acute migraine episodes at the Mike O’Callaghan Federal Medical Center (MOFMC).

3.6.4. Date(s):

August 2015 through August 2017

3.6.5. Source of Research Material:

Source of Research Material per Migraine (Procedures)	# Routine Care	# Research Driven	# Total Procedures
Medical Record Review	0	1	1
Acupuncture	6	0	6
Questions: Pain Severity	12	18	30
Questions: Acupuncture for future pain management	0	6	6
Questions: Preference of acupuncture vs rescue meds	0	6	6
Questions: Rescue medication usage	0	12	12

3.6.6. Subjects:

Male and female (DoD beneficiaries). Age 18 years or older, who currently take rescue medication to treat their acute migraine episodes at the Mike O’Callaghan Federal Medical Center (MOFMC). No other special populations (e.g., children, military basic trainees, prisoners, detainees) will be recruited.

3.6.7. Inclusion/Exclusion Criteria:

Inclusion:

- Male and female DoD beneficiaries, age 18 years or older, who have been previously prescribed rescue medication to treat their acute migraine episodes.

Exclusion:

- Pregnant
- Absence of ear

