4.9.4. Injury Compensation: N/A

4.9.5. Data Safety Monitoring:

The principal investigator will be responsible for the protocol safety monitoring. The PI will make study documents (e.g., consent forms, data pulls) and pertinent hospital or clinical records readily available for inspection by the local IRB and oversight staff for confirmation of the study data.

5.0. Alternatives:

Acupuncture for migraine is done in the Family Medicine Residency as part of standard of care. Subjects may choose to get this type of acupuncture without participating in this study.

6.0. Data Analysis:

6.1. Outcome Measures:

Primary outcome: Reduction of migraine headache pain from mild, moderate or severe to pain free, 20-30 minutes, 2 hours, 4 hours and 24 hours post treatment. Secondary outcomes: patient global assessment of preference for trying acupuncture vs rescue medications; overall satisfaction and perceived effectiveness of the treatment; reduction of symptoms other than migraine headache pain; and use of rescue medication within 12 hours of the initial treatment (irrespective of which study treatment received). These standardized outcome measures are commonly used in comparative effective trials of migraine rescue medications. Researchers will document the points used, and data will be aggregated to determine overall effectiveness. Sub-group analysis by points will be performed to determine if there is more usefulness in 1 point or combination of points.

6.2. Sample size estimation/power analysis:

We will treat 30 subjects. We will administer up to 6 acupuncture treatments for up to 6 different migraine episodes per subject over the course of 3 months. We will not formally test a hypothesis. Rather, we will determine the proportion of migraines that resolve (as assessed by headache severity) 20-30 minutes, 2 hours, 4 hours, and 24 hours after the start of an acupuncture treatment. These data will be used to inform power calculations for future studies.

6.3. Statistical Analysis:

We will use descriptive statistics to characterize the clinical response of subjects after acupuncture treatments.

6.4 Number of Subjects:

Number of subjects planned for MOFMC	Enrolled in Study	60	to result in	30	completing the study.
--------------------------------------	-------------------	----	--------------	----	-----------------------

TOTAL NUMBER OF SUBJECTS (nation-wide/study-wide): 60

7. **Duration of Study:** Approximate duration of the study: 2 years

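### The pain-free proportions at 2, 4 and 24 hours have no rule for rescue medication, so headaches cleared by rescue count as resolved after acupuncture

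*Combined protocol and SAP*

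**What the plan says.** **Outcome.** Section 6.1 makes freedom from pain at 20-30 minutes, 2, 4 and 24 hours the primary outcome. Section 6.2 gives the quantity to be reported: "we will determine the proportion of migraines that resolve (as assessed by headache severity) 20-30 minutes, 2 hours, 4 hours, and 24 hours" after treatment starts. Section 6.3 promises descriptive statistics only. None of the three says how an episode with rescue medication is counted.

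**Rescue.** Section 3.6 (Migraine Episode) states: "If after 20-30 minutes these patients have not had resolution of their headache, they may take their standard of care rescue medication". The screening instructions in the same section tell subjects to hold headache medication until after the visit.

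**Aim and use.** Section 3.2: "We will estimate the magnitude of effect that acupuncture has as an alternative to medication for treatment of acute migraine". The Brief Summary says the estimates will feed power calculations for a randomized trial that "directly compares the effectiveness of Rescue Acupuncture with medical management of acute migraine with rescue medication".

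**What is recorded.** The visit list in section 3.6 asks about rescue twice per episode: for the preceding 7 days at the visit, and at the 24-hour call, "Record type and amount of rescue medications (over-the-counter and prescription) used since acupuncture". Neither item asks for a dose time. Section 3.6.1 describes measuring pain level and "doses of analgesics taken before intervention and at 20-30 minutes, 2 hours, 4 hours, and 24 hours post treatment". The table in section 3.6.5 gives a total of 12 for "Questions: Rescue medication usage". On lost contacts, section 3.6 says "Patients with missed phone calls will not be withdrawn from the study".

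**Related secondary outcome.** Section 6.1 lists rescue use within 12 hours of treatment. It is not linked to the primary outcome.

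**The concern.** Rescue is not a rare deviation here. It is permitted for every episode that acupuncture has not resolved by 20-30 minutes, and subjects bring their medication to the visit. With severity as the sole criterion, the 2-, 4- and 24-hour proportions combine two things: headaches that cleared without medication, and headaches that acupuncture did not clear and medication did. That is not the effect of acupuncture as an alternative to medication.

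The proportions are the main product of this study, and they are meant for planning a trial in which rescue medication is the comparator. A pilot rate that already contains the comparator's effect would mis-size that trial.

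The analysis cannot fully repair this later. If dose times are not collected, the data cannot show whether a subject who was pain-free at 2 hours had taken rescue before or after that call.

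**Working it through.** **1. Which record of rescue use do the documents support?** Section 3.6 allows up to 6 episodes per subject.

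| Item | Per episode | x 6 | Section 3.6.5 total |
|---|---|---|---|
| Pain severity (visit list) | 5 | 30 | 30 |
| Rescue use, visit list (past 7 days; at 24 h) | 2 | 12 | 12 |
| Rescue use, 3.6.1 read as all five time points | 5 | 30 | 12 |

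The table reproduces the visit list. It does not reproduce the fuller reading of 3.6.1. The three places must be reconciled.

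**2. What can be recovered under the visit list?** Let N be the number of episodes. At time t, let A be those with severity 0 and no rescue reported at 24 h, and B those with severity 0 and some rescue reported at 24 h.

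- At 2 h and 4 h the rescue-free rate lies between A/N and (A + B)/N, a width of B/N. Example with assumed counts N = 180, A = 54, B = 25: 54/180 = 30.0% to 79/180 = 43.9%.
- At 24 h the recall period ends at the assessment, so the rate is A/N if the call is completed.
- If the 24-hour call is missed, post-treatment rescue is unknown for the whole episode.
- The 20-30 minute rate precedes permitted rescue and is not affected.
- The 12-hour secondary outcome cannot be derived reliably, because a dose reported at 24 h may have been taken before or after hour 12.

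**3. How large is the overstatement?** Let e be the share pain-free without rescue, r the share of the rest who take rescue, and s the share of those who are pain-free at the time point.

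Reported rate = e + (1 - e) x r x s, so excess = (1 - e) x r x s.

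The documents give none of these. Assumed ranges: e 0.2 to 0.3, r and s 0.3 to 0.7.

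- Smallest: 0.7 x 0.3 x 0.3 = 0.063, or 11 of 180 episodes.
- Largest: 0.8 x 0.7 x 0.7 = 0.392, or 71 of 180.
- Middle (e = 0.3, r = s = 0.5): 0.7 x 0.5 x 0.5 = 0.175, so 30% is reported as 47.5%.

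The 180 is a ceiling: 30 treated subjects (section 6.2) x 6 episodes.

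**4. Against sampling error.** The 95% half-width is 1.96 x sqrt(p(1 - p)/n) at p = 0.475. With n = 180 independent episodes it is 7.3 points. With n = 30, as if each subject supplied one independent unit, it is 17.9 points. The middle-case bias of 17.5 points is well above the first and about equal to the second.

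**5. Effect on the later trial.** Two proportions, two-sided 5%, 80% power, pooled-variance formula. Comparator rates are assumed.

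| Comparator | Per arm planned on 47.5% | Per arm needed on 30% | Result |
|---|---|---|---|
| 20% | 46 | 294 | undersized |
| 40% | 686 | 356 | oversized |
| 50% | about 6,275 | 93 | oversized |

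The direction of the error depends on the comparator rate.

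**The case against.** The study is exploratory, tests no hypothesis and disclaims a definitive answer, so no stated sample size, alpha or power is wrong. That is correct, but the proportions are what the study delivers and their meaning must be fixed.

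Severity regardless of rescue can be a legitimate target: acupuncture first, medication if needed. Section 3.6 says acupuncture is used in the clinic both alone and alongside rescue medication. But the plan does not declare that choice, and the wording of 3.2 points the other way. Reporting both figures meets the objection.

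The bounding problem holds only if the visit list governs. If 3.6.1 is followed in full, rescue status at 2 and 4 hours would be known. This stands as a condition. The counting rule would still be missing.

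The sample-size rows are fragile, and this also stands in part:

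- A 20% comparator sits poorly with s = 0.5. With s = 0.2 the reported rate is 0.3 + 0.7 x 0.5 x 0.2 = 37%, and the comparison becomes 110 against 294 per arm: same direction, smaller error.
- The 6,275 arises because 50% lies only 2.5 points from 47.5%.
- A superiority test is assumed, whereas the stated purpose (section 3.1) would also allow non-inferiority.

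The lower end of the bias range is likewise a matter of assumption. Taking e = 0.4, r = 0.25 and s = 0.2 gives 0.6 x 0.25 x 0.2 = 3 points.

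**Conclusion.** The concern holds and must be fixed. Applied as written, sections 6.1 and 6.2 count rescue-cleared headaches as resolved at 2, 4 and 24 hours, against the objective in 3.2. The direction is certain: a rate that includes these headaches cannot be below the rescue-free rate and exceeds it whenever rescue clears any headache. The size is not known from the documents. Under the assumptions shown it is 6 to 39 points, with 17.5 in the middle case, which can match or exceed the sampling error. The sample-size rows show only that planning could err in either direction; they do not predict by how much.

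The limit to bounds at 2 and 4 hours follows from the visit list and the 3.6.5 table, and would close under the full reading of 3.6.1. The 20-30 minute proportion is sound on this point.

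**What to change.** **Outcome wording (6.1, 6.2).** At each time point, define pain-free as severity 0 with no rescue medication since acupuncture. Count an episode with rescue before that time point as not pain-free. Report severity 0 regardless of rescue as a supplementary line, so that the acupuncture-then-rescue result is also visible.

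**Data collection.** Reconcile the visit list, 3.6.1 and 3.6.5 with one another and with the 12-hour outcome, including whether 3.6.1 intends a separate rescue item at 20-30 minutes. Ask about rescue use at the existing 2- and 4-hour calls, and record the time of the first dose at whichever of the 2-, 4- or 24-hour contacts it is reported. A missed 24-hour call then no longer affects the 2- and 4-hour rates. It would still leave the 24-hour rate unknown, and the 12-hour outcome too unless rescue had already been reported, so state how such episodes are handled.

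**Cost.** Two more rescue questions per episode (4 x 6 = 24 per subject instead of 12), one dose time per episode with rescue, and revised wording and table. No new contacts, and no change to when subjects may take rescue. The reported proportions will be lower.
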